8.3 Prior and Concomitant Medications

Prior and concomitant medications will be coded using the World Health Organization Drug Dictionary (WHO-DD), version 03-2016 and will be classified according to the default Anatomical Therapeutic Chemical (ATC) classification system code (up to 4 levels), WHO-DD Drug Name, and Preferred Term (PT).

Due to the nature of this study, the date and time of first dose of study drug was not collected on the CRF. Therefore, the following algorithm will be used to determine prior medications:

- Earliest Possible Medication Start Date \leq Day 1 (Baseline) Visit Date

The following algorithm will be used to determine concomitant medications:

- Latest Possible Medication Stop Date \geq Day 1 (Baseline) Visit Date

Depending on the start and stop dates of the medication, it is possible for a medication to be classified as both prior and concomitant.

Prior and concomitant medications will be summarized by the ATC Class Level 3 category (or Level 2 if there is not an applicable Level 3 category) and PT. Subjects may have more than one medication per ATC category and PT. At each level of subject summarization, a subject will be counted once if he/she reports one or more medications at that specific level.

The prior medication frequency distribution table will be displayed by each study drug treatment period received and all subjects even though the prior medication information was collected prior to dispensing study drug. The concomitant medication frequency distribution table will be displayed by the study drug treatment period based on the earliest possible start date described in [Section 5.6.3](#) and prior medications that are not stopped on the Day 1 (Baseline) visit.

9. Pharmacodynamic Analyses

A horizontal bar chart illustrating the percentage of the population aged 15-24 in 2010 across different countries. The y-axis lists 29 countries, and the x-axis shows the percentage from 0% to 100%. The bars are color-coded by region: Latin America and the Caribbean (light blue), Europe (light green), Asia and the Pacific (light orange), and Africa (light pink). The chart shows significant regional variation, with countries like India, China, and Mexico having the highest percentages (around 60-70%), while others like Japan and Sweden have the lowest (around 10-20%).

Region	Country	Percentage (%)
Latin America and the Caribbean	Argentina	65
	Bolivia	60
	Brazil	65
	Chile	60
	Colombia	65
	Ecuador	60
	El Salvador	65
	Guatemala	60
	Honduras	65
	Peru	60
Europe	Austria	65
	Belgium	60
	Bulgaria	65
	Croatia	60
	Czech Republic	65
	Denmark	60
	Estonia	65
	Finland	60
	France	65
	Germany	60
Asia and the Pacific	Greece	65
	Hungary	60
	Iceland	65
	India	65
	Ireland	60
	Italy	65
	Japan	15
	Jordan	65
	Korea	60
	Luxembourg	65
Africa	Malta	65
	Morocco	60
	Mexico	65
	Netherlands	60
	New Zealand	65
	Norway	60
	Oman	65
	Poland	60
	Portugal	65

A high-contrast, black and white image showing a series of horizontal bars. The bars are mostly black, with white spaces between them. The bars are of varying lengths and are set against a white background. The image is heavily processed, appearing as a binary black and white pattern.

[figure not shown]
10.3

Aptinyx Inc.

Protocol No.: NYX-2925-2002

[figure not shown]
Statistical Analysis Plan (SAP)

Aptinyx Inc.

Protocol No.: NYX-2925-2002

[figure not shown]
Statistical Analysis Plan (SAP)

Aptinyx Inc.

Protocol No.: NYX-2925-2002

[figure not shown]
Statistical Analysis Plan (SAP)

Aptinyx Inc.

Protocol No.: NYX-2925-2002

Statistical Analysis Plan (SAP)

Aptinyx Inc.

Protocol No.: NYX-2925-2002

[figure not shown]
Statistical Analysis Plan (SAP)

A large black rectangular redaction box covers the majority of the page content, starting below the header and ending above the footer. The redaction is irregularly shaped, with jagged edges and some white space visible at the top and bottom.

Aptinyx Inc.

Protocol No.: NYX-2925-2002

[figure not shown]
Statistical Analysis Plan (SAP)

Aptinyx Inc.

Protocol No.: NYX-2925-2002

[figure not shown]
Statistical Analysis Plan (SAP)

[figure not shown]

Aptinyx Inc.

Protocol No.: NYX-2925-2002

Statistical Analysis Plan (SAP)

12. Safety Analyses

12.1 Adverse Events

Treatment-emergent adverse events (TEAEs) will be those occurring during or after administration of the first dose of study drug until 30 days after the final dose of study drug. The date and time of first dose of study drug was not collected on the CRF for all subjects. Therefore, the following algorithm will be used to determine if the adverse events are treatment-emergent without a date and time of first dose of study drug:

- Earliest Possible AE Start Date \geq Day 1 (Baseline) Visit and Study Drug Dispensation **and**
- Latest Possible AE Start Date \leq 30 Days After the Final Dose of Study Drug

AEs that started prior to first dosing of study drug, but become worse in severity after receiving study drug will be considered treatment-emergent. The determination of whether or not an adverse event is classified as “treatment emergent” (i.e. TEAE) is not determined by the classification of “relationship

to study drug" collected on the CRF, but rather by the temporal relationship of the adverse event to the administration of study drug.

A related study drug TEAE is defined as any TEAE with at least a possible relationship to the study drug as assessed by the investigator or that is missing the assessment of causal relationship whose relationship to the study drug could not be ruled out. Relationships of "possibly related", "probably related", or missing are collected on the CRF, then those adverse events will be considered related study drug TEAEs. If the "unrelated" or "unlikely related" are collected on the CRF, then those adverse events will be considered not related study drug TEAEs.

Severity is assigned to each adverse event collected on the CRF. Maximum severity has the following order: "life threatening", "severe", "moderate", and "mild" as possible collection options on the CRF. A missing severity will be treated as "unknown" for analysis purposes.

All adverse events will be coded and summarized by System Organ Class (SOC) and Preferred Term (PT) based on Medical Dictionary for Regulatory Activities (MedDRA) version 19.0 coding dictionary. This data will be summarized in a frequency distribution. Subjects may have more than one TEAE record per SOC and PT. At each level of subject summarization, a subject will be counted once if he/she reports one or more TEAE record at that specific level. For tables summarized by SOC and PT, the events will be displayed in the order of descending frequency counts for all treatments by SOC and then PT within SOC.

The number of subjects with at least one of the following adverse events, percentages for each category by treatment, and the number of total events will be included in an overall treatment-emergent adverse events summary table:

- Any TEAEs
- Related TEAEs
- Maximum Severity TEAEs
- Serious TEAEs
- Related, Serious TEAEs
- TEAEs Leading to Study Discontinuation
- Related TEAEs Leading to Study Discontinuation
- TEAEs Leading to Death

[figure not shown]
Summaries including the number of subjects and percentages of the following adverse events by SOC and PT will be provided:

- Any TEAEs
- Related TEAEs
- Maximum Severity TEAEs
- Serious TEAEs
- TEAEs Leading to Study Discontinuation

Additionally, TEAEs will be summarized by descending frequency counts of PT for all treatments. All adverse event data collected will be provided in subject listings. Subset subject listings will also be provided by serious treatment-emergent adverse events and deaths; by treatment-emergent adverse events leading to study discontinuation; any adverse events that are not considered to be treatment-emergent; by serious adverse events and deaths that are not considered to be treatment-emergent; and by adverse events leading to study discontinuation that are not considered to be treatment-emergent.

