4.6 Analyses Changes from the Protocol

In Section 12.6.1 of the protocol, it states that TEAE summaries will be provided separately for each study period and the follow-up period. TEAEs will be summarized and grouped based on the last study drug treatment the subject received compared to the start date of the event explained in [Section 5.2](#). The rest of the analyses stated in the protocol support the analyses planned in this SAP.

5. General Statistical Principles

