5.3 Treatment Group Comparisons

The following treatment groups will be summarized in the statistical tables:

- Placebo
- NYX-2925 20 mg PO QD
- NYX-2925 200 mg PO QD
- All Doses of NYX-2925
 - Pooled for adverse events, concomitant medications, and study drug treatment compliance and exposure tables.
- Not Treated
 - This will only be displayed for the analysis population table that presents subjects screened, but were not enrolled in the study or dispensed study drug.
- All Subjects
 - This will only be displayed for the analysis population and concomitant medications tables.

The following changes in treatment period comparisons will be performed for efficacy:

- Change from Baseline
- Change from Week 2 [REDACTED]
- Change from Week 4 [REDACTED]
- Change from Week 6 [REDACTED]

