5.6.3 Missing or Partial Dates

Adverse Event Start Dates:

- Method 1 – Earliest Possible Start Date:
 - If any combination of the year, month, and/or day are missing then the start date will be set to the earliest possible date that is \geq to the screening date.
- Method 2 – Latest Possible Start Date:
 - If any combination of the year, month, and/or day are missing then the start date will be set to the latest possible date that is \leq to the latest possible adverse event end date. If the adverse event is ongoing after the final visit for the subject, then the final visit date will be used.

Prior/Concomitant Medications Start Dates:

- Method 1 – Earliest Possible Start Date:
 - If any combination of the year, month, and/or day are missing then the start date will be set to the earliest possible date that is \geq to the subject’s date of birth.
- Method 2 – Latest Possible Start Date:
 - If any combination of the year, month, and/or day are missing then the start date will be set to the latest possible date that is \leq to the latest possible medication end date. If the medication is ongoing after the final visit for the subject, then the final visit date will be used.

Adverse Event and Prior/Concomitant Medications End Dates:

- Method 1 – Earliest Possible End Date:
 - If any combination of the year, month, and/or day are missing then the end date will be set to the earliest possible date that is \geq to the earliest possible adverse event/medication start date.
- Method 2 – Latest Possible End Date:
 - If any combination of the year, month, and/or day are missing then the end date will be set to the latest possible date that is \leq to the subject's final visit date. If the adverse event/medication is ongoing after the final visit for the subject, then the final visit date will be used.

Medical History Disease Onset Dates:

- If year is missing, then the date will not be imputed.
- If both the month and day are missing, then the date will be imputed as July 1st with the year collected. However, if this imputed date is \geq to the screening date then the imputed date will be the screening date minus 1 day.
- If only the day is missing, then the date will be imputed as the 15th with the year and month collected. However, if this imputed date is \geq to the screening date then the imputed date will be the screening date minus 1 day.

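### SAP 12.1 leaves an on-treatment AE with an incomplete start date out of the TEAE tables when its earliest possible start falls before Day 1, unless worsening is recorded

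*SAP*

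**What the plan says.** SAP 12.1 describes TEAEs in words as events "occurring during or after administration of the first dose of study drug until 30 days after the final dose of study drug". Protocol 12.6.1 likewise relies on onset after study drug, or on later worsening of an existing AE. Because first-dose times were not collected, SAP 12.1 turns this into two conditions that must both hold. The lower one is "Earliest Possible AE Start Date \geq Day 1 (Baseline) Visit and Study Drug Dispensation". The upper one caps the latest possible start at 30 days after the final dose.

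SAP 5.6.3 supplies the two dates. Under Method 1, if any part of the date is missing, the missing parts "are missing then the start date will be set to the earliest possible date that is" on or after screening. Under Method 2 they "are missing then the start date will be set to the latest possible date that is" no later than the latest possible end date, or the final visit if the AE is ongoing.

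There is one other route into the tables: "AEs that started prior to first dosing of study drug, but become worse in severity after receiving study drug will be considered treatment-emergent". AEs that fail go to a listing of "any adverse events that are not considered to be treatment-emergent".

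For the treatment columns, SAP 4.6 says "TEAEs will be summarized and grouped based on the last study drug treatment the subject received", judged against the event's start date. SAP 5.2 labels the time before Day 1 as no treatment. SAP 5.3 lists placebo, each dose, and an all-doses column ("Pooled for adverse events, concomitant medications, and study drug treatment compliance and exposure tables").

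**The concern.** The screening date is always before Day 1, so Method 1 can place an incomplete start before Day 1 even when the true onset was on treatment. The lower condition then fails. The worsening clause does not rescue an AE of constant severity. The written definitions are silent on uncertain dates, but the algorithm settles every such case as non-emergent, including cases whose true onset meets the definition.

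Elsewhere the SAP settles doubt the other way. Concomitant medication is judged by its latest possible stop date (SAP 8.3), a missing causality assessment counts as related (SAP 12.1), and subjects who did not return all their drug are assumed to have been dosed (SAP 6.1).

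What is at stake is the completeness of the TEAE tables, including those for related events, serious events and events leading to discontinuation. With about 24 subjects, one reclassified serious event can change a row.

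**Working it through.** The documents give no figure on this point, so there is none to reproduce.

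**Single case.** Screening 20 February 2018, Day 1 on 12 March 2018, true onset 20 March 2018 (20 - 12 + 1 = Day 9), recorded as 'March 2018'.
- Earliest possible start = the later of 1 March and 20 February = 1 March.
- 1 March is before 12 March, so the AE is not a TEAE, although it began on Day 9.
- Had it begun in April and been recorded as 'April 2018', the earliest start would be 1 April and it would be a TEAE.

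**Inputs for the enumeration.**
- Day 1: every date from 1 June 2017 to 13 October 2018, 500 dates, so that Day 49 falls by November 2018 (protocol synopsis).
- True onset: Days 1-49, each equally likely (assumption). This gives 500 x 49 = 24,500 cases.
- Periods by true onset: placebo Days 1-14, 20 mg Days 15-28, 200 mg Days 29-49. Follow-up is counted with 200 mg, the last drug received (SAP 4.6).
- AE ongoing at the final visit, last dose on Day 42, no worsening (assumptions).

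**Rule.** Earliest = the later of the first date compatible with the record and screening. An AE is lost if earliest < Day 1. The upper condition removes nothing for a completer, because Method 2 caps the latest start at the final visit (Day 49), before Day 42 + 30.

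**Only the day missing.**

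| True period | Cases | Lost | Share |
|---|---|---|---|
| Placebo | 7,000 | 5,306 | 76% |
| 20 mg | 7,000 | 2,125 | 30% |
| 200 mg and follow-up | 10,500 | 36 | 0.3% |
| All | 24,500 | 7,467 | 30.5% |

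The lost AEs are those whose onset shares a calendar month with Day 1, unless Day 1 is the first of the month. Placebo comes first, so 5,306 / 7,467 = 71% of them are true placebo-period onsets. The length of screening makes no material difference. Other assumptions move the overall share modestly: 36% if onsets cluster early in each period, and 35% if only Days 1-42 are counted, with Day 1 between July 2017 and June 2018.

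**More missing.** With month and day missing, 95% are lost (93% if Day 1 dates are confined to one calendar year). With the whole date missing, the earliest start is screening and 100% are lost.

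**Share of all TEAEs.** If a share q of AEs lack only the day, the overall loss is q x 0.305. For q = 1%, 5% and 10% this is 0.3%, 1.5% and 3.0%. The documents do not give q.

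**Effect on the period comparison.** The table above uses true onset, which the analyst does not have. Columns must be set from an imputed date, and neither SAP 4.6 nor SAP 5.2 says which. Let r be the count shown in a column divided by its true count, among AEs lacking the day. The 200 mg to placebo event ratio is then multiplied by (1 - q + q x r for 200 mg) / (1 - q + q x r for placebo).
- Columns by earliest possible start: r = 0.358 for 200 mg and 0.980 for placebo, because later AEs move back into placebo. At q = 5%: (0.95 + 0.05 x 0.358) / (0.95 + 0.05 x 0.980) = 0.969. For q = 1%, 5% and 10% the ratio falls by 0.6%, 3.1% and 6.2%.
- Columns by latest possible start: r = 1.620 and 0. At q = 5%: (0.95 + 0.05 x 1.620) / 0.95 = 1.085. The ratio rises by 1.6%, 8.5% and 18%.

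**The case against.** The strongest objection is that this is a convention and a small one. Neither definition says how to treat an uncertain date, so no text is strictly contradicted. Protocol 9.5.2 asks for start and stop dates and visits are weekly, so incomplete dates should be few, and those lacking the month rarer still. No safety testing is planned (SAP 5.4.3), and non-emergent AEs, including serious ones and those leading to discontinuation, have their own listings. Most tables count a subject once per term, so a lost event alters a cell only if it was that subject's only one there. All of this stands and sets the severity. It does not make the rule sound: AEs that meet the plan's own onset definition are still left out, and a listing does not restore a table count.

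A reader might infer more: since most lost AEs began on placebo, NYX-2925 would look worse against placebo. The documents do not support that. The inference sorts AEs by their true onset, which is unknown for exactly these records. The SAP does not name the imputed date that sets the column, and the ratio falls under one choice and rises under the other. The only imputed-date column rule the SAP states is for concomitant medication (SAP 8.3), and it uses the earliest start, under which the ratio falls.

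It is also fair to object that rewording the lower condition alone would not settle the period comparison. With earliest-date columns, the recovered AEs have assigned dates in the no-treatment interval of SAP 5.2, for which SAP 5.3 lists no AE column. With latest-date columns, the ratio would still be inflated by 7.6% at q = 5%. The fix therefore has to say where these AEs are counted.

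**Conclusion.** The point holds, as a minor one. As written, SAP 12.1 and 5.6.3 remove on-treatment AEs from all TEAE tables when the start date is incomplete and its window opens before Day 1, unless worsening is recorded. Among such on-study AEs the loss is about 30% with the day missing, 93-95% with month and day missing, and 100% with no date, assuming uniform onset over Days 1-49 and no worsening. Against all TEAEs it is 0.3-3.0% if 1-10% of AEs lack the day. That range is assumed and the true share is probably small.

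No direction of bias between NYX-2925 and placebo can be claimed. What can be said is that the treatment column for these AEs is undefined.

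**What to change.** In SAP 12.1, class an AE as non-emergent only if its latest possible start (5.6.3 Method 2) is before Day 1, or its earliest possible start is more than 30 days after the final dose. Keep the worsening clause. Flag AEs with an incomplete start date in the AE listing.

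Count AEs whose possible start window opens before Day 1, or spans more than one treatment period, in the overall TEAE totals, and show them in a separate 'period uncertain' row or column. They are then neither dropped as untreated nor credited to one period. SAP 5.3 confines its all-subjects column to two other tables, so the AE tables need an overall column for this.

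In the enumeration the reworded rule loses no on-study AE. It uses dates the SAP already derives and needs no new data. The cost is some reprogramming and a change to the table shells. It also lets in some pre-dose AEs with incomplete dates and no known end before Day 1: about 67% of those lacking only the day (48% with a 30-day screening period, 81% with 7-14 days), 97-99% of those lacking month and day, and all of those with no date. If the AE is known to have ended before Day 1, none are let in. That error is conservative for safety, and the flag keeps it visible.

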7.4. Subject Withdrawal Criteria

Subjects who withdraw from the NYX-2925 treatment period will not be replaced. Any subject may withdraw consent at any point during the study. The investigator can discontinue a subject at any time if it is deemed medically appropriate, or for subject noncompliance with study requirements. Subjects will be withdrawn from the study if any of the following criteria are met:

[REDACTED]

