9.5.5. Action Taken for Adverse Events

For each reported AE, an investigator must document the action taken according to the following criteria:

- No action taken
- Concomitant medication taken
- Hospitalization or prolongation of hospitalization
- Discontinued study
- Nondrug therapy
- Other (specify)

The investigator must also document the action taken in regards to IP (as a result of a given AE) according to the following criteria:

- Dose not changed
- IP interrupted
- IP withdrawn
- Not applicable
- Unknown

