11. INDIVIDUAL STOPPING CRITERIA

Subjects will be withdrawn from the treatment period of the study if the following laboratory results are confirmed by repeat testing. Repeat testing must be completed within 48-72 hours:

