12.6.1. Adverse Events

A treatment-emergent AE (TEAE) is defined as an AE with an onset that occurs after receiving study drug, or a continuing AE diagnosed prior to the date of first dose of study drug, which increases in severity after the start of dosing. Adverse events will be categorized by system organ class and preferred term with the Medical Dictionary for Regulatory Activities.

Summary tables for TEAEs will include numbers and percentages of subjects experiencing TEAEs by system organ class and preferred term. If a subject has more than 1 TEAE that codes to the same preferred term, the subject will be counted only once for that preferred term. Similarly, if a subject has more than 1 TEAE within a system organ class category, the subject will be counted only once in that system organ class category.

The following TEAE summaries will be provided for each study period (placebo, NYX 2925 20 mg, NYX-2925 200 mg, and follow-up:

- Overall summary of TEAEs,
- TEAEs by system organ class and preferred term,
- Drug-related TEAEs by system organ class and preferred term,
- TEAEs by system organ class, preferred term, and severity.

Serious TEAEs, and TEAEs leading to study drug discontinuation will be identified.

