12.6.2. Clinical Laboratory Tests

Clinical laboratory results considered clinically important by the investigator will be identified.

Individual results of clinical laboratory tests from hematology, serum chemistry, and urinalysis outside of the normal range will be flagged in the data listings.

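### SAP 12.1 reports adverse events leading to study discontinuation, where protocol 12.6.1 promises to identify those leading to study drug discontinuation, and SAP 4.6 does not mention the difference

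*SAP*

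**What the plan says.** Protocol 12.6.1 lists four TEAE summaries to be given for each study period and then adds: "Serious TEAEs, and TEAEs leading to study drug discontinuation will be identified". SAP 12.1 is the section that puts this into practice. Its overall table has a row for "TEAEs Leading to Study Discontinuation" and a second row for the drug-related subset. The same category returns as one of the summaries by system organ class and preferred term. It also defines two subset listings: one "by treatment-emergent adverse events leading to study discontinuation", and one for events that led to study discontinuation but were not treatment-emergent.

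SAP 4.6, which records departures from the protocol, cites protocol 12.6.1 by number. It declares one change, to how TEAEs are grouped by treatment, and then states: "The rest of the analyses stated in the protocol support the analyses planned in this SAP".

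The protocol records the two kinds of stopping separately. In section 9.5.5, leaving the study is one option under the general action taken for an event. The section then adds: "The investigator must also document the action taken in regards to IP (as a result of a given AE) according to the following criteria". Withdrawal of the drug is an option in that second list. Section 7.4 says "Subjects will be withdrawn from the study if any of the following criteria are met", whereas section 11 says "Subjects will be withdrawn from the treatment period of the study if the following laboratory results are confirmed by repeat testing".

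**The concern.** Stopping the drug and leaving the study are different events. The first bears on tolerability of the drug. The second also depends on whether the subject stays for follow-up and on how the site completes the form. The protocol singles out the first, and the readable SAP reports only the second.

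Safety is this trial's secondary objective, and this is the first study of the drug in fibromyalgia. A reader of the study report who takes the SAP 12.1 discontinuation row as the count of adverse events that stopped the drug could get a number that is too low. Nothing in SAP 4.6 would warn that reader that the category had changed.

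**Working it through.** The plan gives no figure on this point, so the check sets the texts side by side.

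**1. Which category each readable item uses**

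| Place | Items on discontinuation | Category |
|---|---|---|
| Protocol 12.6.1 | one sentence; events to be identified | study drug |
| SAP 12.1, overall table | 2 rows (any, related) | study |
| SAP 12.1, summaries by class and term | 1 | study |
| SAP 12.1, subset listings | 2 (treatment-emergent, not treatment-emergent) | study |

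SAP 12.1 therefore has 2 + 1 + 2 = 5 readable items on study discontinuation and none on study drug discontinuation.

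**2. Substitution or missing detail?** The protocol sentence names two kinds of event: serious ones and those that stop the drug. For serious TEAEs, SAP 12.1 supplies an overall row, a summary by class and term, and a subset listing. For the second kind it supplies the same three forms of output, with the category changed. That pattern is a substitution, not a promise left without detail.

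**3. Can the categories differ for one subject?** Crossing the two items in protocol 9.5.5 gives four cases for a TEAE:

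| Drug withdrawn for the event | Study discontinued for the event | In the protocol's category | In the SAP's rows |
|---|---|---|---|
| yes | yes | yes | yes |
| yes | no | yes | no |
| no | yes | no | yes |
| no | no | no | no |

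The second case is the one at issue. The readable protocol suggests a route to it. Section 9.5.1 requires a laboratory abnormality to be treated as an adverse event if it is independent of the underlying condition and leads to interruption or discontinuation of the drug. Section 11 withdraws subjects from the treatment period on confirmed laboratory results. Together they allow an adverse event that ends treatment without necessarily being recorded as ending study participation. The criteria under sections 7.4 and 11 are not visible and could narrow this route.

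The third case is also possible in form. SAP 12.1 counts events as treatment-emergent up to 30 days after the final dose, so an event in the follow-up week could end participation when there is no drug left to stop.

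**4. Is the difference declared?** SAP 4.6 addresses the relevant protocol section, declares only the grouping change, and says that the remaining protocol analyses support the SAP. For this item the readable SAP text does not bear that out.

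**The case against.** The strongest reply is that the protocol asks only that these events be identified. They are not among its four TEAE summaries, and section 12.6.2 uses the same verb with no table attached: "Clinical laboratory results considered clinically important by the investigator will be identified". SAP 12.1 lists all adverse event data collected, and protocol 9.5.5 requires the action on the drug to be documented for each event. A reader could therefore find these events in a planned output, and the study-discontinuation items could be seen as additions, which protocol 12.2 permits.

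Much of this stands. A reader might infer that the protocol requires a table by class and term for drug-stopping events; it does not. A reader might also infer that such events would disappear from the report. They would not: the full listing keeps them. The SAP 7.1 disposition listing shows the date of last dose, the date of completing or discontinuing the study, completion status and primary reason, so a gap between stopping drug and leaving the study would be visible. SAP 7.1 also counts completion of each treatment period, and SAP 8.2 summarises exposure by last-dose date.

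It is also fair that the problem case is not shown to occur. No readable text describes follow-up after early stopping of the drug. SAP 5.5.1 maps the follow-up form to an early termination visit from Day 2 onward, and both items in protocol 9.5.5 can be completed for the same event. In this trial the two categories may coincide.

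The reply does not remove the mismatch. Leaving the reader to search the full listing is weaker than what the SAP gives the other half of the same protocol sentence. The visible text of SAP 7.1 does not tie the reason for discontinuation to an adverse event term.

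**Conclusion.** The mismatch is real and minor. On the readable text, SAP 12.1 reports adverse events leading to study discontinuation where protocol 12.6.1 names study drug discontinuation, and SAP 4.6 is silent on it. A subject whose drug is stopped for an adverse event, but who is not recorded as leaving the study, would not be counted in any of the five discontinuation items in SAP 12.1.

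The number of such subjects is unknown and may be zero. No percentage is attached, because the overall table is presented by treatment and its denominators depend on who is treated in each period. All safety summaries are descriptive, so no test is affected, and neither are the imaging analyses.

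The conclusion assumes that the two items in protocol 9.5.5 are collected as described. It is also confined to the readable text. The planned list of tables and listings is redacted and the mock shells are a separate document, so a drug-discontinuation output may exist there. A reader might infer that the analysis has been omitted altogether; the documents do not support going that far.

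**What to change.** In SAP 12.1, add to the overall table a row for TEAEs leading to study drug discontinuation, and add a matching subset listing. Derive both from the action on the drug recorded under protocol 9.5.5, using the option for withdrawal and not the one for interruption. Keep study discontinuation as its own category, with its present rows and listings. A further summary by class and term is optional. If the sponsor prefers not to add these outputs, or if they already exist in the redacted list, SAP 4.6 or 12.1 should say so.

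The cost is one table row and one listing, from an item the protocol already requires for every adverse event. With about 24 subjects planned, both may be empty or repeat the study-discontinuation outputs.
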